4.5.11 Post-treatment Survival

Post-treatment survival, in addition to PROs and anti-cancer treatments, will be collected via telephone calls and/or clinic visits every three months until death, loss to follow-up, or study termination by the Sponsor.

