4.6.2 Patient Discontinuation from Study

Patients have the right to voluntarily withdraw from the study at any time for any reason. In addition, the investigator has the right to withdraw a patient from the study at any time. Reasons for withdrawal from the study may include, but are not limited to, the following:

- Patient withdrawal of consent
- Patient non-compliance, defined as failure to comply with protocol requirements as determined by the investigator or Sponsor

- Study termination or site closure

Every effort should be made to obtain information on patients who withdraw from the study. The primary reason for withdrawal from the study should be documented on the appropriate eCRF. If a patient requests to be withdrawn from the study, this request must be documented in the source documents and signed by the investigator. Patients who withdraw from the study will not be replaced.

If a patient withdraws from the study, the study staff may use a public information source (e.g., county records) to obtain information about survival status.

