OS is defined as the time from study treatment initiation to death from any cause. For patients who are alive at the time of analysis data cut-off, OS time will be censored at the date the patient was last known to be alive. Survival time for patients with no post-baseline survival information will be censored at one day after the study treatment initiation date. Kaplan-Meier methodology will be used to estimate median OS and Kaplan-Meier curves will be provided.

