7. DATA COLLECTION AND MANAGEMENT

7.1 DATA QUALITY ASSURANCE

A contract research organization (CRO) will be responsible for data management of this study, including quality checking of the data. Data entered manually will be collected via EDC through use of eCRFs. Sites will be responsible for data entry into the EDC system. In the event of discrepant data, the CRO will request data clarification from the sites, which the sites will resolve electronically in the EDC system.

The Sponsor will perform oversight of the data management of this study. The CRO will produce eCRF Specifications for the study based on Sponsor's templates including quality checking to be performed on the data.

Central laboratory data will be sent directly to the Sponsor, using the Sponsor's standard procedures to handle and process the electronic transfer of these data.

The eCRFs and correction documentation will be maintained in the EDC system's audit trail. System backups for data stored by the Sponsor and records retention for the study data will be consistent with the Sponsor's standard procedures.

The eCRFs are to be completed through use of a Sponsor-designated EDC system. Sites will receive training and have access to a manual for appropriate eCRF completion. eCRFs will be submitted electronically to the Sponsor and should be handled in accordance with instructions from the CRO.

All eCRFs should be completed by designated, trained site staff. The eCRFs should be reviewed and electronically signed and dated by the investigator or a designee.

At the end of the study, the investigator will receive patient data for his or her site in a readable format on a compact disc that must be kept with the study records. Acknowledgement of receipt of the compact disc is required.

The PRO data will be collected on paper questionnaires. The data from the questionnaires will be entered into the EDC system by site staff.

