## **2. STATISTICAL HYPOTHESES**

There is no formal statistical study hypothesis. All statistical analyses will be entirely descriptive.

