## **5. STATISTICAL ANALYSES**

### **5.1 GENERAL CONSIDERATION**

A primary study analysis that includes analyses of all efficacy endpoints and safety summaries will be conducted based on data collected up to 6 months after the last patient is enrolled in the study (last patient in [LPI]). The final study analysis including updated analyses of safety and efficacy endpoints will be conducted based on data collected up to 24 months after LPI.

Unless otherwise indicated, efficacy analyses will be based upon the Evaluable population in each cohort consisting of all enrolled patients who received study medication and have at least two post-baseline tumour assessments for response evaluation. Analyses of safety, survival, corticosteroid use, and time to subsequent intracranial or systemic anti-cancer treatment endpoints will be conducted based upon the Safety evaluable population in each cohort consisting of all patients who received at least one dose of study medication. Analyses of patient-reported outcome (PRO) endpoints will be conducted based upon the PRO-evaluable population.

Any incomplete or missing death date will be handled separately for safety and efficacy analyses. In safety analyses, all deaths will be included, regardless of completeness of death date; patients who died with a partial or missing death date will be included as an event. In efficacy analyses, a death is considered an event only if a complete death date is available; patients who died with only a partial or missing death date will not be considered as a death event.

Based on the results of the primary analysis for Study CO39722 (IMspire170) of cobimetinib plus atezolizumab combination in previously untreated advanced BRAFV600 wild-type melanoma patients (see Section 1.3.2.4 of the study protocol), enrollment in the BRAFV600 wild-type cohort was discontinued. The primary endpoint will not be evaluated on Cohort 1. Only a subset of analysis on efficacy secondary endpoints will be performed.

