#### **5.4.2.4 Intracranial, Extracranial and Overall Progression-Free Survival – RECIST**

Intracranial, extracranial, and overall progression-free survival (PFS) are defined as the time from study treatment initiation to the first occurrence of disease progression, as

determined by the investigator according to RECIST v1.1, or death from any cause, whichever occurs first. Data for patients who have not experienced disease progression or death at the time of analysis data cutoff will be censored at the last evaluable tumor assessment date.

Kaplan-Meier methodology will be used to estimate median intracranial, extracranial, and overall PFS. Kaplan-Meier curves will be provided. The 95% CI of the median PFS will be constructed using the Brookmeyer and Crowley method (Brookmeyer and Crowley 1982).

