#### **5.4.2.7 Overall Survival**

The overall survival (OS) analysis will be based on the safety population (all treated patients) only.

OS is defined as the time from study treatment initiation to death from any cause. For patients who are alive at the time of analysis data cutoff, OS time will be censored at the date the patient was last known to be alive.

Kaplan-Meier methodology will be used to estimate OS. Kaplan-Meier curves will be provided. The 95% CI of the median OS will be constructed using the Brookmeyer and Crowley method.

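### SAP 5.1 does not count a known death with an incomplete date as an efficacy event, which biases Kaplan-Meier OS upward on average if such deaths occur

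*SAP*

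**What the plan says.** Protocol 6.4.2 gives the endpoint: "OS is defined as the time from study treatment initiation to death from any cause". SAP 5.4.2.7 keeps that definition, estimates OS by Kaplan-Meier and bases it on all treated patients.

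SAP 5.1 treats incomplete death dates differently by type of analysis. Safety analyses count every death, whether or not the date is complete. Efficacy analyses require a complete date: "patients who died with only a partial or missing death date will not be considered as a death event".

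The censoring rules do not mention these patients. SAP 5.4.2.7 says: "For patients who are alive at the time of analysis data cutoff, OS time will be censored", at the date last known alive. Protocol 6.4.2 adds censoring at day 1, but only for patients with no survival information after baseline. For PFS, SAP 5.4.2.4 says: "Data for patients who have not experienced disease progression or death at the time of analysis data cutoff will be censored", at the last evaluable tumour assessment, and DOR follows PFS. Neither document has an imputation rule for death dates or an OS sensitivity analysis. SAP Appendix 1, which lists changes from the protocol's analyses, covers only time to deterioration.

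**The concern.** A missing day or month makes the time of death uncertain, not the fact of death. SAP 5.1 accepts this for safety but removes the same death from OS, the endpoint defined by death from any cause.

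Kaplan-Meier assumes that a censored patient has the same future risk as those still at risk. Here the patient is censored because of a death that occurred but was not fully dated. The estimator then spreads that patient's weight over people who live longer. The study has no control arm, so the OS estimate is read at face value and no second arm carries an offsetting error.

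**Working it through.** Neither document states an expected number of deaths, an OS assumption or a count of incomplete death dates. There is no planned figure to reproduce, so the check covers direction first and then size under stated assumptions.

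**1. One patient followed through the rules.** A treated patient is known to have died before cutoff, month known, day unknown.

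| Rule | Result |
|---|---|
| Safety, SAP 5.1 | counted as a death |
| Efficacy, SAP 5.1 | not a death event |
| OS population, SAP 5.4.2.7 | stays in (all treated) |
| OS censoring, SAP 5.4.2.7 | written for patients alive at cutoff; the only date it names is last known alive |

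The patient is in the analysis and is not an event, so the natural reading is censoring at the date last known alive.

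**2. Direction, by hand.** Ten patients die at months 1 to 10.
- All deaths counted: S(5.5) = 5/10 = 0.500 and S(6.5) = 4/10 = 0.400.
- Month-6 death censored at 3.2 months: S(3.5) = 7/10. Six are then at risk, so S(5.5) = 0.7 × 5/6 × 4/5 = 0.467. Nothing happens at month 6, so S(6.5) = 0.467.

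The curve is higher from the true death time onward (0.467 against 0.400) and slightly lower just before it (0.467 against 0.500). The first time S reaches 0.5 or below is month 5 in both cases, so this one death does not move the median.

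**3. Inputs for size.**
- n = 60: planned Cohort 2 enrolment (Protocol 6.1).
- Cutoff 24 months after last patient in (SAP 5.1). Accrual 48 − 24 = 24 months, from the 48-month study length in Protocol 3.2.
- True median m = 10, 14 or 24 months. Protocol 1.1 gives about 10 to 24 for one study of combined BRAF and MEK inhibition; 14 is an assumed middle value.
- Last contact on a three-month grid (Protocol 4.5.11).
- Assumed: exponential OS, uniform accrual, affected deaths random, and k = 1 or 5 of them.

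**4. Rough formula.** Expected deaths are D = 60 × [1 − (2^(−24/m) − 2^(−48/m)) / (24 ln 2 / m)]:
- m = 10: 60 × [1 − (0.1895 − 0.0359)/1.6636] = 54.5
- m = 14: 60 × [1 − (0.3048 − 0.0929)/1.1883] = 49.3
- m = 24: 60 × [1 − (0.5 − 0.25)/0.6931] = 38.4

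Under an exponential model the median is ln 2 × follow-up / deaths. Leaving k deaths uncounted multiplies it by about D/(D − k), a shift of m × k/(D − k). This ignores the small follow-up lost.
- k = 1: 10/53.5 = 0.19; 14/48.3 = 0.29; 24/37.4 = 0.64 months
- k = 5: 50/49.5 = 1.01; 70/44.3 = 1.58; 120/33.4 = 3.59 months

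**5. Kaplan-Meier simulation.** Each trial is analysed with all deaths counted, then with k deaths censored at the last three-monthly contact. The median is averaged over adjacent event times when S equals 0.5.

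| Affected deaths | Mean shift in median OS, true median 10 / 14 / 24 (months) | Rise in 24-month OS (points) |
|---|---|---|
| 0 | none | none |
| 1 | +0.13 / +0.19 / +0.63 | 0.5 to 0.9 |
| 5 | +0.92 / +1.53 / +3.56 | 2.8 to 4.5 |

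These are averages. With one affected death the median does not rise in 31–45% of simulated trials. Taking the median as the first time S ≤ 0.5 gives larger shifts (one death +0.27 / +0.39 / +0.92; five +1.16 / +1.85 / +4.04). The averaged-median shifts lie inside the typical 95% CI of the median: 6.8–14.1, 9.4–19.8 and 16.4–33.0 months.

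**6. PFS.** Progression before death still counts. Suppose 10–20% of events are death first and 5–10% of those dates are incomplete. Then 60 × 0.10 × 0.05 = 0.3 to 60 × 0.20 × 0.10 = 1.2 patients are affected. With an assumed median of 5.5–7 months, simulated median PFS rises by 0.4% to 1.7%.

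**7. Error from imputing instead, five affected deaths.** For patients still in three-monthly contact, the earliest permitted date shifts median OS by −0.13 / −0.16 / −0.17 months and the latest by +0.15 / +0.16 / +0.18. If contact ended long before death (last known alive uniform between treatment start and death), the earliest date shifts it by −0.64 / −0.87 / −1.00. Censoring at last known alive in that case shifts it by +0.68 / +1.10 / +2.89.

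**The case against.** The strongest defence is that the affected set may be empty. Protocol 5.3.5.8 sends deaths to dedicated forms or immediate reporting, and Protocol 5.6 puts later deaths on a long-term follow-up form. Survival data "will be collected via telephone calls and/or clinic visits every three months until death, loss to follow-up, or study termination by the Sponsor". Protocol 7.1 adds: "In the event of discrepant data, the CRO will request data clarification from the sites". One conceivable source is withdrawn patients, for whom "the study staff may use a public information source (e.g., county records) to obtain information about survival status", but that such records lack a full date is conjecture. The counts of one and five are assumptions. All of this stands, and it limits the severity.

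The rule is also deliberate and open. SAP 5.1 announces that safety and efficacy differ, so a reader who finds fewer deaths in OS than in the safety summary of SAP 5.6.2 has not found a contradiction. OS is supportive, and "All statistical analyses will be entirely descriptive".

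Two stronger readings are tempting but unsupported. A reader might infer that OS is inflated whenever such a death occurs. The hand example and the 31–45% of trials with no rise in the median show that only an average shift is supported. A reader might also infer that the handling is wholly open, so that the patient could be dropped or censored at the cutoff. Dropping conflicts with the all-treated population in SAP 5.4.2.7, and would not have a fixed direction: with one such death the median falls in 17–45% of trials. No OS rule censors at the cutoff. The gap is narrower: the censoring date for these patients is implied, not stated.

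**Conclusion.** The point holds and is minor. SAP 5.1 drops known deaths from an endpoint defined by death from any cause. On the natural reading it replaces them with informative censoring at the date last known alive, which biases Kaplan-Meier OS upward on average. PFS and DOR are affected only where death comes first. The primary endpoint, independently reviewed intracranial response, and the sample size are untouched.

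The size depends on a number that the documents do not give. With no such death there is no effect. Under the stated assumptions one death moves the median by about +0.1 / +0.2 / +0.6 months, and five by about +0.9 / +1.5 / +3.6, for true medians of 10 / 14 / 24 months. The direction on average does not depend on those assumptions; the magnitudes do.

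**What to change.** Replace the efficacy sentence in SAP 5.1 with:

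> Every known death by the cutoff is an event in OS, and in PFS and DOR when no progression came first. An incomplete death date is imputed within any known month or year, after the date last known alive and no later than the earlier of the cutoff and the date the death was reported.

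Pre-specify one default, for example the 15th when only the day is missing and otherwise the midpoint of the permitted interval. Report the number of imputed dates. Require, not merely allow, a sensitivity analysis at the earliest and latest permitted dates. Imputation error is shown to be small only for patients still in three-monthly follow-up. For the others, an earliest-date default could swap an upward bias for a downward one.

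The cost is a few lines of SAP text and minor programming, with no new data. OS may look slightly less favourable. If no death date is incomplete, nothing changes.

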### **5.2 PARTICIPANT DISPOSITION**

The analysis of patient disposition will be based on the safety population.

Study enrollment and reasons for study discontinuation will be summarized by cohort. Study treatment administration and reasons for discontinuation from study treatment will be summarized.

### **5.3 PRIMARY ENDPOINT ANALYSIS**

The primary endpoint will be derived and analyzed on Cohort 2 only.

### **5.3.1 Definition of Primary Endpoint**

Intracranial objective response rate (ORR) is defined as the proportion of patients with a complete or partial response in their intracranial disease based on two consecutive assessments  $\geq 4$  weeks apart. Disease status will be determined by an IRC according to RECIST v1.1 with a modified measurability definition for intracranial lesions ( $\geq 0.5$  cm by MRI) and allowing up to five intracranial target lesions.

### **5.3.2 Main Analytical Approach for Primary Endpoint**

The primary efficacy analysis will be the analysis of the intracranial ORR. The intracranial ORR will be presented together with a 95% Pearson-Clopper CI using the evaluable population.

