6.4 EFFICACY ANALYSES

There is no formal statistical study hypothesis. All efficacy analyses will be entirely descriptive with 95% CIs will be provided where applicable.

The primary efficacy analysis population will be the Evaluable Patient population in BRAF^{V600} mutation-positive cohort consisting of all enrolled patients who received study medication and have at least two post-baseline tumour assessments for response evaluation. Patients in the BRAF^{V600} wild-type cohort may not be evaluable as per this definition and will be analysed descriptively.

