6.4.1 Primary Efficacy Endpoint

The primary efficacy objective is to evaluate the intracranial ORR in the BRAF^{V600} mutation-positive study cohort. Intracranial ORR is defined as the proportion of patients with a complete or partial response in their intracranial disease based on two consecutive assessments ≥ 4 weeks apart. Disease status will be determined by an IRC according to RECIST v1.1 with a modified measurability definition for intracranial lesions (≥ 0.5 cm by MRI) and allowing up to five intracranial target lesions. Data for patients with no post-baseline intracranial tumour assessment will be excluded from efficacy analyses. For intracranial response rate, a 95% Pearson-Clopper CI will be calculated and presented.

A sensitivity analysis of the primary endpoint that includes patients with unconfirmed CR or PR will also be conducted in each cohort based upon the Safety population in order to detect a potential bias with regard to the primary analysis.

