## **STATISTICAL ANALYSIS PLAN AMENDMENT RATIONALE**

Key changes to the SAP, along with the rationales for each change, are summarized below.

Section	Description of Change	Rationale for Change
4	Patient-reported outcome (PRO)-evaluable population added for the PRO analysis	It is stated in the protocol that “Only patients with a non-missing baseline assessment and at least one non-missing post-baseline assessment will be included in PRO analyses.” For clarify purpose, we added PRO population in the Section 4 and clarified that this population will be used for PRO analysis to ensure compliance with the protocol.
5.1	Only a subset of efficacy analysis will be done on Cohort 1	Given that the recruitment of Cohort 1 was stopped prematurely, it is no longer appropriate to produce all the efficacy analysis due to small sample size. Thus, the Statistical Analysis Plan is updated to limit the efficacy analysis.
5.3.1	No analysis on primary endpoint on Cohort 1	After the premature discontinuation of Cohort 1, it was decided to not perform the independent review of scan for patients in Cohort 1. Thus, all analyses on the primary endpoint will be performed on Cohort 2 only.
5.3.3	Adding sensitivity analysis of primary endpoints on all treated patients (safety population)	The analysis on primary endpoint is planned on evaluable population only, which excludes subjects with less than 2 scans. Excluding these subjects could lead to an inflation of the response rate by excluding the early progression or death. Therefore, we add an analysis on all treated patients to assess the bias introduced by excluding these patients.
5.3.4.1	New subgroup	Additional subgroup added to better explore the effect of demographic characteristics and clinical and biological prognostic factors on the efficacy endpoint.
5.4	Adding analysis secondary efficacy endpoints on all treated patients (safety population)	The analysis on efficacy endpoint (objective response rate [ORR], progression-free survival [PFS], and disease control rate [DCR]) are planned on evaluable population, which excludes subjects with less than 2 scans. Excluding these subjects could lead to an inflation of the response rate by excluding the early progression or death. Therefore, we add an analysis on all treated patients to assess the bias introduced by excluding these patients.

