#### 4. ANALYSIS SETS

The following populations are defined:

Population	Definition
Safety-evaluable Population	All participants received at least one dose of study treatment (e.g., atezolizumab, cobimetinib, or vemurafenib)
Evaluable Population	All enrolled patients who received study medication and have at least two post-baseline intracranial tumour assessments for response evaluation
PRO-evaluable Population	All patients who received any amount of any study medication (e.g., atezolizumab, cobimetinib, or vemurafenib) and have a baseline and at least one post baseline PRO assessment in the questionnaire of interest (EORTC QLQ-C30 or EORTC QLQ-BN20)

EORTC QLQ-C30 and QLQ-BN20=European Organization for Research and Treatment of Cancer Quality of Life questionnaire core questionnaire and brain cancer specific module; PRO=patient-reported outcome.

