### **5.3.3 Sensitivity Analyses for Primary Endpoint**

Sensitivity analyses of the primary endpoint will be conducted in order to detect a potential bias with regard to the primary analysis.

- The analysis on primary endpoint will be replicated on Safety evaluable population to assess the response rate of all patients enrolled and treated in this study.
- The intracranial ORR will include patients with unconfirmed complete response (CR) or partial response (PR) based on the safety population. Unconfirmed Intracranial ORR will be analyzed using the same methods as described in Section 5.3.2.

In addition, a summary of concordance between investigator and IRC intracranial response assessments, according to RECIST v1.1 with a modified measurability definition for intracranial lesions ( $\geq 0.5$  cm by MRI) and allowing up to five intracranial target lesions, will be provided.

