## **5.4 SECONDARY ENDPOINTS ANALYSES**

Unless otherwise noted, all efficacy analyses will be performed on both the evaluable patient population and all treated patients (safety population).

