#### **5.4.2.6 Intracranial, Extracranial and Overall Disease Control Rate at 16 Weeks – RECIST**

Intracranial, extracranial, and overall disease control rates (DCR) are defined as the proportion of patients with a CR or PR (based on two consecutive assessments  $\geq 4$  weeks apart) or stable disease (SD) at 16 weeks from study treatment initiation, as determined by the investigator according to RECIST v1.1. The denominator is all patients in the evaluable population.

Week 16 occurs at Study Day 112. Allowing 7 days after the exact Week 16, assessments that occur between Study Day 112 and Study Day 119 (inclusive) will be considered as a Week 16 assessment.

Patients with a CR or PR or SD at 16 weeks from study treatment initiation are patients:

- With a CR or PR assessed within the window of Study Days 112-119 inclusive and followed by a consecutive CR or PR assessment in the next  $\geq 4$  weeks.

OR

- With a CR or PR assessed prior to the Study Day 112 and followed by a consecutive CR or PR assessment in the next  $\geq 4$  weeks and on or after Study Day 112.

OR

- With a SD assessed within the window of Study Days 112-119 inclusive.

DCR will be presented together with a 95% Pearson-Clopper CI.

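### The primary intracranial ORR excludes patients with fewer than two scans, none of whom can be a confirmed responder, so the estimate can only be pushed upward; all treated Cohort 2 patients should be the primary set.

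*SAP*

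**What the plan says.** SAP 5.3.1 defines a responder as a patient whose intracranial disease shows CR or PR, by the independent review committee (IRC), on two consecutive assessments at least four weeks apart. SAP 5.3.2 then sets the analysis: "The intracranial ORR will be presented together with a 95% Pearson-Clopper CI using the evaluable population". Under SAP 4, patients in that population must have been treated and "have at least two post-baseline intracranial tumour assessments for response evaluation". Protocol 6.4 names the same primary set, without the word intracranial: patients must "have at least two post-baseline tumour assessments for response evaluation".

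The SAP amendment rationale recognises the consequence: "Excluding these subjects could lead to an inflation of the response rate by excluding the early progression or death". SAP 5.3.3 responds with a sensitivity analysis in which the primary analysis "will be replicated on Safety evaluable population to assess the response rate of all patients enrolled and treated in this study". A second sensitivity analysis there counts unconfirmed responses on the safety population. The primary set itself was not changed.

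Two other sentences bear on the all-treated analyses:

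- Protocol 6.4.1, repeated in the synopsis, says: "Data for patients with no post-baseline intracranial tumour assessment will be excluded from efficacy analyses".
- For the disease control rate (DCR), SAP 5.4.2.6 says: "The denominator is all patients in the evaluable population". SAP 5.4, however, says that, unless otherwise noted, "all efficacy analyses will be performed on both the evaluable patient population and all treated patients (safety population"), and SAP 5.5.1.8 applies the same DCR method to the safety population.

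**The concern.** The entry condition for the primary set is a precondition of the endpoint. It selects on something that happens after treatment starts, and it can act in one direction only. The first scan falls in the last week of Cycle 2 and the next about eight weeks later. A patient who dies, withdraws or starts another anti-cancer treatment before a second scan is dropped rather than counted as a treatment failure.

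The trial is single-arm and descriptive, so its main product is one response rate with a confidence interval. If any treated patient is excluded, that rate is too high as a statement about treated patients, and the interval is centred on the raised value.

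The planned all-treated analysis is the natural correction, but its wording is not secure. SAP 5.3.3 does not say how patients with zero or one scan are counted. The exclusion sentence in Protocol 6.4.1, read literally, could remove patients with no scan from that analysis too.

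**Working it through.** **Inputs.** About 60 patients enrolled in Cohort 2, 15% study drop-out and about 50 evaluable (Protocol 3.1 and 6.1). Response rates of 35% to 55% in the precision table (Protocol Table 8, SAP Table 2). A 95% Clopper-Pearson interval for the analysis (SAP 5.3.2). Treating either 15% or 10 of 60 as the excluded share f is an assumption, so a range is shown.

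**The plan's own figures.** 50/0.85 = 58.8, rounded up to 59, against the stated approximately 60; and 60 × 0.85 = 51, against approximately 50. The tabulated intervals reproduce as p ± 1.96·√(p(1−p)/50). For p = 0.40 this is 26.4% to 53.6%, as stated, and the other four rows also agree. These are normal-approximation intervals; the planned exact interval for 20/50 is 26.4% to 54.8%.

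**Formula.** Let x be the confirmed responders, N the treated patients and k those with fewer than two scans. None of the k can be among the x. Hence

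evaluable ORR = x/(N − k) = (x/N) × 1/(1 − f), with f = k/N.

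The factor is 1/(1 − 0.15) = 1.18 at f = 15%, and 60/50 = 1.20 at 50 of 60.

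**Worked example.** 24 confirmed responders among 60 treated. Coverage is the chance that the primary 95% interval contains a true all-treated ORR of 40%. It comes from 200,000 simulated trials of 60 patients, in which each non-responder is excluded with probability f/(1 − p). Exact enumeration agrees to within 0.1 point.

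| f | Primary analysis reports | 95% CI | Coverage of 40% |
|---|---|---|---|
| 0 | 24/60 = 40.0% | 27.6–53.5 | 96.4% |
| 5% | 24/57 = 42.1% | 29.1–55.9 | 95.7% |
| 10% | 24/54 = 44.4% | 30.9–58.6 | 92.1% |
| 15% | 24/51 = 47.1% | 32.9–61.5 | 85.3% |
| 16.7% | 24/50 = 48.0% | 33.7–62.6 | 82.2% |

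At f = 15%, coverage is 89.9% for a true rate of 30% and 79.6% for 50%.

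**Across the plan's range, with 50 of 60 evaluable.** A reported 35% corresponds to 35 × 50/60 = 29.2% of treated patients, a gap of 5.8 points. A reported 55% corresponds to 55 × 50/60 = 45.8%, a gap of 9.2 points.

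**The case against.** The strongest reply is that the sponsor has already dealt with this. The SAP names the bias, adds the confirmed ORR on all treated patients, and runs the secondary efficacy analyses on both sets. There is no hypothesis, threshold or power calculation, so no decision rule reads only the evaluable figure. That is fair, and it narrows the point to which estimate carries the primary label. It does not justify giving that label to the figure the SAP itself describes as open to inflation.

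The excluded share may also be small. A scan showing progression must be repeated about four weeks later whether or not treatment continues, and scanning goes on after treatment stops for other reasons unless new anti-cancer therapy starts. Many early progressors will therefore have two scans and stay in as non-responders. This stands: f is unknown, the 15% is a study drop-out rate rather than a rate of having fewer than two scans, and at f = 5% coverage is close to nominal. The direction of the error is unaffected. The coverage figures express the same shift in another form; they are not a second defect.

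Counting a single-scan partial response as a failure can be called conservative. It nevertheless follows from the confirmed endpoint in SAP 5.3.1, and the planned unconfirmed-response analysis shows how much it matters.

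The stated purpose of the all-treated analysis does imply that patients with zero or one scan count as non-responders, and the amendment rationale lists DCR among the endpoints to be run on all treated patients. The two wording conflicts are therefore secondary, but they are real and easily removed.

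**Conclusion.** The concern holds. By construction, the two-scan rule can remove only patients who are not confirmed responders, so the primary ORR is at or above the all-treated ORR and never below it. The size depends on a share the documents do not give: nothing at f = 0, 2.1 points at 5% and 8.0 points at 50 of 60 evaluable, in the example with 24 responders among 60. No test, threshold or power is affected; what changes is the headline estimate and its interval. Because the all-treated analysis is already planned, this should be fixed but is not fatal. The DCR denominator and the protocol's exclusion sentence are lesser inconsistencies on the same theme.

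**What to change.** 1. In SAP 4 and 5.3.2, Protocol 6.4 and 6.4.1, and the synopsis, make all treated Cohort 2 patients the primary ORR set. State that anyone without a confirmed IRC response, including patients with zero or one scan, is a non-responder. Keep the evaluable set as supportive.
2. Delete or reconcile the sentence in Protocol 6.4.1 and the synopsis that excludes patients with no post-baseline intracranial assessment, so that it cannot apply to the all-treated analysis.
3. Reconcile the DCR denominator in SAP 5.4.2.6 with SAP 5.4 and 5.5.1.8.
4. Restate Protocol Table 8 and SAP Table 2 for 60 treated patients with the planned exact interval: 35% (23.1–48.4), 40% (27.6–53.5), 45% (32.1–58.4), 50% (36.8–63.2), 55% (41.6–67.9).

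The cost is an amendment to both documents, because each names the primary set, plus the restated tables. Changing a prespecified primary set late in a single-arm trial needs a dated justification; the SAP's own acknowledgement of inflation provides the reason. No new data are needed. The headline ORR will be lower if there are confirmed responders and any treated patient has fewer than two scans.
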